8 STATISTICAL ASPECTS

8.1 Number of necessary subjects

The study published on the costs of DMD in Portugal [1] was based on a sample of 46 patient/caregiver pairs without justification for the sample size. The international study collected data from 100-200 patients per country [6]. In France, as of March 1, 2022, the BMDMR (National Registry of Patients with Rare Diseases) reported 2,028 DMD patients. While it is not possible to rely on the French cost data collected by Cavazza et al. 2016, which is based on only two patients [4], we can examine other countries where the values are not aberrant and where there is generally a coefficient of variability (sd/m) of 1. The sample size for a precision of 15% is thus 171 patient/caregiver pairs according to the recommendations of Johnston et al. 2019 [11]. The chosen method of telephone interviews assumes that there will be no non-responses, and since this is a cross-sectional study without randomization, interviews will continue until this number is reached. Stratification in terms of sex, age, and location will be performed, and then families will be randomly selected within each stratum to obtain a representative sample of the BNDMR population. The a priori number of strata is 16 (2 (sex) x 4 (age groups) x 2 (annual follow-up at center vs. no regular follow-up)).

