5.3 Patients identification in BNDMR

The CO BNDMR will provide the URC ECO with a secure file listing eligible patients identified by a specific identifier (ID_étude), as well as the variables of interest for sampling and the rare disease site considered.

The patient identification period runs from the start date of inclusions in the BNDMR (2017) to January 1, 2023.

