5.4 Recruitment methods and feasibility

A random sample of patients will be drawn upon receipt of the CO BNDMR file by the URC ECO. The URC ECO will contact the sampled centers to inform them of the study project, the number of eligible patients in their center and their study ID, and will provide them with the associated documents (protocol, information letter to be given to the patient). Follow-up centers will be able to return to CO BNDMR to obtain the BaMaRa ID of sampled patients, in order to retrieve their contact in the application. Once they have been properly identified by the center, patients and/or their primary caregivers will be contacted by the CRA of their follow-up center, via an information letter explaining the purpose and modalities of the study. The questionnaire will be sent to them in the same letter, so that they can familiarize themselves with it and to give them time to gather the necessary information (expenses, etc.). The main caregiver will then be identified during the call following this letter.

With the BNDMR reporting a preliminary enrolment of around 2,028 DMD patients as of March 1, 2022 [9], the feasibility of the number of subjects required for this study will be ensured.

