6.3.2 Questionnaire answering

The questions are taken from published questionnaires, and a validation of the questionnaire's comprehensibility and acceptability will be carried out on at least 2 child/caregiver and 2 adult/caregiver patients before the information letters are sent out [10].

The standardized questionnaire (see appendix) will be sent to patient/caregiver pairs with the information letter. This will enable participants to gather the information they need to answer the questionnaire.

A clinical research associate from the center which usually cares for the DMD patient or, failing that, from the URC Eco, will then contact the patient and/or his/her main carer by telephone. The interview, lasting a maximum of half an hour, will be based on the questionnaire and will ensure that the participant has understood the questions and that all the required data have been collected.

Variables intended to ensure representativeness or to enable sample adjustment will be collected at inclusion, including commune of residence (used only for adjustment), as well as:

- Patient characteristics: gender, month and year of birth, ambulatory or non-ambulatory status;
- Characteristics of the main caregiver: age, sex, relationship to the patient (degree of kinship, partner or other non-family relationship), family structure (couple, characteristics of other children, etc.).

Variables for cost analysis will also be collected (see chapter 7 + appended questionnaire).

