9 RIGHTS OF ACCESS TO DATA AND SOURCE DOCUMENTS

9.1 Collected Data

In the first phase (Phase 1), the sampling variables will be communicated by the BNDMR (study pseudonym, age, sex, place of residence, care site, age at diagnosis). In the second phase (Phase 2), the data necessary for this study will be collected through questionnaires directly from the participants and will be entered by a clinical research associate into an electronic data collection notebook (eCRF) developed using the CleanWeb™ solution (Telemedicine Technologies).

As this is a cross-sectional study, the interview serves as inclusion. A participant who refuses the interview will therefore not be considered included. Participants may request to withdraw from the study during the interview, and the questionnaire will then be incomplete: if the subject does not oppose it, the data collected up to that point will be retained and analyzed.

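### Section 8.1 names one set of sampling strata and counts another, sets no target per stratum, and section 8.3 does not use the strata in the mean or its interval

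*Combined protocol and SAP*

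**What the plan says.** Section 8.1 states that "Stratification in terms of sex, age, and location will be performed", with families then drawn at random within each stratum so that the sample represents the registry. The following sentence reads "The a priori number of strata is 16 (2 (sex) x 4 (age groups) x 2 (annual follow-up at center", the other level being no regular follow-up. The four age bands and the number to be drawn per stratum are not given. On when to stop, 8.1 says only that "interviews will continue until this number is reached", meaning the total of 171 pairs.

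Other sections bear on this:

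- 5.3: the registry file will carry study identifiers, "as well as the variables of interest for sampling and the rare disease site considered".
- 5.4: "A random sample of patients will be drawn upon receipt of the CO BNDMR file by the URC ECO".
- 9.1: the sampling variables are itemised as "study pseudonym, age, sex, place of residence, care site, age at diagnosis".
- 6.3.2: "Variables intended to ensure representativeness or to enable sample adjustment will be collected at inclusion, including commune of residence (used only for adjustment"). The list that follows includes "Patient characteristics: gender, month and year of birth, ambulatory or non-ambulatory status" and caregiver characteristics.
- 8.3: costs are summarised by means, variances and confidence intervals, and also by mobility level. Strata and weights are not mentioned.
- 8.4: pairs who do not respond are replaced in a way that keeps the sample representative; no mechanism is given.
- 8.5: a detailed SAP will be written before database freeze.
- 12.2: questionnaire data will not be matched with registry data.

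**The concern.** The draw cannot be carried out as written. Location is named but not counted; follow-up regularity is counted but not named, and it is absent from the one itemised list of what the registry will supply. Two teams following 8.1 could draw different samples.

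The second issue is that nothing ties the achieved sample to the strata. With a stopping rule on the total alone and no stratum targets, strata that respond readily can fill up at the expense of others. The main criterion is a mean annualised cost, so its value depends on the sample's composition wherever stratum means differ. Section 2.1 gives reason to expect a difference by age: published costs rose with severity, particularly with ambulatory status, and walking is lost on average in early adolescence.

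The third issue is that 8.3 stratifies the draw but not the analysis. It neither corrects an unbalanced sample nor takes the precision that a balanced one would give.

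**Working it through.** **1. The plan's own figures.** Inputs from 8.1: coefficient of variation 1, relative precision 15%. The confidence level is not stated; 95% two-sided is assumed because it reproduces the result.

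- n = (1.960 × 1 / 0.15)² = 170.73, rounded up to **171**. Reproduced.
- Achieved half-width: 1.96/√171 = 0.1499, or **15.0%**.
- Strata: 2 × 4 × 2 = **16**. Reproduced, but only with follow-up as the third factor.

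**2. The third factor, section by section.**

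| Place | Location | Follow-up regularity |
|---|---|---|
| 8.1, named factors | yes | no |
| 8.1, count of 16 | no | yes |
| 9.1, registry variables | residence and care site | not listed |
| 6.3.2, listed adjustment variables | commune | not listed |

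**3. Proportional allocation.** The sampling fraction is 171/2,028 = 8.4%, or about 1 in 11.9. The plain mean is then self-weighting apart from non-response. Any stratum with fewer than about 12 registry patients would expect less than one pair. The documents give no stratum sizes.

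**4. Size of a composition shift (illustration only).** Table 1, Portuguese study, non-medical plus indirect cost. The total column is not used, because the non-ambulatory total of 19,993 EUR is below the sum of its own components.

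- Ambulatory: 11,890 + 4,395 = 16,285 EUR.
- Non-ambulatory: 29,717 + 10,211 = 39,928 EUR.
- Difference: 23,643 EUR.

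Assume, as an upper case, that the age bands separate the two groups completely. A 10-point gap between sample and population share moves the plain mean by 0.1 × 23,643 = 2,364 EUR. With an assumed non-ambulatory share p, the mean is 16,285 + p × 23,643. The between-group share of variance at CV 1 is p(1−p) × 23,643² / mean², and the stratified half-width is 0.1499 × √(1 − share).

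| p (assumed) | Mean, EUR | 2,364 as % of mean | Between-group share | Stratified half-width |
|---|---|---|---|---|
| 40% | 25,742 | 9.2% | 0.202 | 13.4% |
| 50% | 28,107 | 8.4% | 0.177 | 13.6% |
| 60% | 30,471 | 7.8% | 0.144 | 13.9% |

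Under these assumptions an interval that ignores the strata reports 15.0% where 13.4% to 13.9% would be correct for a proportional sample.

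**5. Price of weighting back an unbalanced sample.** Assume a 50/50 population and equal standard deviations. The design effect is Σ W²/s, where W is the population share and s the sample share.

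- Sample 60/40: 0.25/0.6 + 0.25/0.4 = 1.042; half-width 0.1499 × √1.042 = **15.3%**.
- Sample 70/30: 0.25/0.7 + 0.25/0.3 = 1.190; half-width 0.1499 × √1.190 = **16.4%**.

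Both are before any gain from stratification.

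**The case against.** The best defence is that the plan's intention is clear enough. It aims for a representative sample, keeps that aim on replacement (8.4), collects variables for adjustment (6.3.2) and promises a SAP (8.5). The generic wording of 5.3 could cover follow-up regularity. The text is also a partial translation, so location might loosely mean place of follow-up. This supports reading the allocation as proportional. It does not reconcile the two lists, since regularity of visits is not a place, and it supplies no targets, replacement mechanism or estimator.

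Four stronger readings are tempting, and the documents do not support them:

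- *The contradiction biases the mean by 8-9%.* Sex and age are in both lists. The illustration concerns age and ambulation, not the disputed factor, and the documents give no costs by location or follow-up.
- *The sample size is wrong.* The figure of 171 reproduces, and under proportional allocation it stands.
- *A later SAP cannot repair the draw.* It could reweight on gender, birth date and commune, at the modest price shown above. It could not recover empty strata or lost precision.
- *Section 12.2 makes follow-up regularity unusable at analysis.* That holds only if the variable exists solely in the registry file. The appended questionnaire is not available to check.

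Nor does the statement that commune is used only for adjustment rule out location as a stratum: it concerns the questionnaire item, while 9.1 lists residence from the registry.

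**Conclusion.** The point holds. The inconsistency in 8.1 is certain, and the missing stratum targets, replacement mechanism and stratified estimator are plain from the text. The numerical consequence is conditional. If the achieved sample is proportional, the plain mean is nearly unbiased apart from non-response and the unstratified interval is somewhat too wide. If it is not proportional and stratum costs differ, the plain mean shifts. The 7.8% to 9.2% per 10-point gap, against a planned precision of 15%, is an upper-case illustration that rests on Portuguese costs, complete separation of ambulatory groups by age band, and assumed shares of 40% to 60%. The effect of location versus follow-up remains unquantified. The plan should be corrected before the draw, because the correction costs little then and part of the loss cannot be recovered later.

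**What to change.** Before requesting the registry extract, rewrite 8.1 with one set of strata, the four age bands, a proportional target per stratum, and replacement by random draw within the same stratum.

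- **Simplest choice:** sex × age × two levels of place of residence. This keeps 16 strata (171/16 = 10.7 pairs on average; proportional cells will vary around this). All three variables are in 9.1 and can be recovered from gender, birth month and year, and commune in 6.3.2. It does not balance on follow-up regularity.
- **If follow-up regularity is kept:** confirm that the registry holds it, add it to 9.1, and carry the registry-defined stratum code into the eCRF at inclusion after confirming that this is compatible with 12.2. Self-report should not stand in for it: it may disagree with the registry class from which the weights are built, and 12.2 would prevent a check.

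In 8.3, estimate the mean as Σ (N_h/N) × stratum mean, with the stratified variance and N_h counted in the eligible registry file. Fix beforehand a rule that merges any stratum with fewer than two respondents into the adjacent age band.

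The cost is wording and a standard estimator. Weighting may widen the interval slightly if the sample is unbalanced (15.0% to 15.3% in the 60/40 example), and it does not remove non-response bias within strata.

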8.2 Population

All the participants surveyed will constitute the analysis population.

8.3 Statistical methods

Cost data will be described in terms of means, variances, and confidence intervals. The normality or non-normality of the cost distributions will be checked. Costs (direct and indirect) will be described among patients living as of December 31, 2023. Analyses will also be conducted by level of mobility.

8.4 Method for Handling Missing Data

It is not planned to compare non-respondents with respondents but to solicit new patient/caregiver pairs while maintaining representativeness with respect to the BNDMR population. The number of missing data will be limited by constructing short and explicit questionnaires and through the direct interview method conducted by a clinical research associate. In the case of missing data during the completion of the survey, or if the interview is interrupted, follow-ups may be organized if the family has given their consent.

8.5 Exclusion of Data in Statistical Analysis. Management of Changes Made to the Analysis Plan

A detailed statistical analysis plan will be drafted before the database is frozen. It will take into account any modifications to the protocol or any unexpected events that occur during the study and impact the analyses presented above. Planned analyses may be supplemented in accordance with the study objectives. Any subsequent changes to the statistical analysis plan must be justified and will result in a new version of the document. These deviations from the analysis plan will be reported in the final study report. All documents will be kept in the study file.

8.6 Person Responsible for the Analyses

Data analysis will be conducted by a statistician from the URC Eco under the supervision of [name].

9 RIGHTS OF ACCESS TO DATA AND SOURCE DOCUMENTS

9.1 Collected Data

In the first phase (Phase 1), the sampling variables will be communicated by the BNDMR (study pseudonym, age, sex, place of residence, care site, age at diagnosis). In the second phase (Phase 2), the data necessary for this study will be collected through questionnaires directly from the participants and will be entered by a clinical research associate into an electronic data collection notebook (eCRF) developed using the CleanWeb™ solution (Telemedicine Technologies).

As this is a cross-sectional study, the interview serves as inclusion. A participant who refuses the interview will therefore not be considered included. Participants may request to withdraw from the study during the interview, and the questionnaire will then be incomplete: if the subject does not oppose it, the data collected up to that point will be retained and analyzed.

9.2 Source Documents

Source documents are defined as any original document or object that proves the existence or accuracy of a data point or fact recorded during the clinical study. This will include the questionnaires completed by the patient/caregiver pairs included in the study. They will be kept for the duration of the study and until the completion of data analysis, and then archived for 5 years from the date of questionnaire completion.

9.3 Data Confidentiality

Individuals with direct access to the data will take all necessary precautions to ensure the confidentiality of information related to participants, particularly regarding their identity and the results obtained.

These individuals, like the investigators themselves, are subject to professional secrecy (as defined by Articles 226-13 and 226-14 of the Penal Code). During the research, the data collected on participants and transmitted to the sponsor by the investigators (or any other specialized participants) will be coded.

Under no circumstances should the names of the individuals concerned or their addresses be clearly displayed. Only the first letter of the subject's last name and the first letter of their first name will be recorded, accompanied by a coded number specific to the study indicating the order of inclusion of the subjects.

10 CONTROL AND QUALITY ASSURANCE

10.1 Qualification of Participants

The coordinating investigator, the qualified person, or the scientific officer ensures that the research participants are qualified for the tasks assigned to them.

10.2 Data Quality

A review of the data at the end of the interview by the Clinical Research Associate (CRA) and the patient will allow for checking their consistency and ensuring that no omissions have occurred. A data management plan will be established to determine consistency checks. Descriptive analyses will be conducted on available data, assuming that missing data are non-informative, and the counts of missing values will be described for each variable, if applicable.

11 ETHICAL CONSIDERATIONS

11.1 Role of the Sponsor

The Assistance Publique - Hôpitaux de Paris is the sponsor of this research, and by delegation, the Delegation for Clinical Research and Innovation (DRCI) carries out its missions in accordance with Article L.1121-1 of the Public Health Code. The Assistance Publique - Hôpitaux de Paris reserves the right to interrupt the research at any time for administrative reasons.

11.2 Information for Subjects and Right to Withdraw

In accordance with Article L1121-1-1 of the Public Health Code, no non-interventional research may be conducted on a person who has opposed it after being provided with the information required by Article L1122-1 of the same code. Patients and their caregivers will be fully and fairly informed, in terms understandable to the general public, about the objectives, their rights to oppose their participation in the study, and the possibility of withdrawing at any time. All this information is included in an information form provided to the patient and their caregiver.

12 DATA MANAGEMENT AND CONSERVATION

12.1 Observation Notebook

The observation notebook will only include the data necessary for analysis for publication. Other patient-related data necessary for follow-up outside the study will be compiled in their medical file. An electronic observation notebook (eCRF) will be used for data collection.

12.2 Data Management

The responsibility for processing the project is ensured by AP-HP (Direction des Services Numériques (DSN) for Phase 1 and Direction de la Recherche Clinique et de l'Innovation (DRCI) for Phase 2). The project team within the DSN is represented by the following members of the BNDMR operational unit:

- [name] [name], Medical Director
- [name], Chief Data Officer
- [name], Project Manager

The party responsible for implementing the processing is the Direction de la Recherche Clinique et de l'Innovation (DRCI) within AP-HP, represented by [name]. The Data Protection Officer (DPO) is [name], within the DSI of AP-HP, [name], email: [contact], [contact].

The data collected from the questionnaires administered to patients will not be matched with the BNDMR data; the two databases will remain distinct from the beginning to the end of the study.

A data collection notebook will be created under CleanWeb™ for entering data from the questionnaires administered to patients. CleanWeb™ is a secure, controlled web-access solution for creating structured forms (eCRF) for manual information entry (Electronic Data Capture - EDC); this solution, complementary to EDS, is used by AP-HP for electronic management of clinical studies. The eCRF will be developed under the responsibility of a data manager. Only authorized individuals may access the eCRF through a secure login (username and password).

The data collected will be entered by a CRA into the eCRF at the time of the interview. The eCRF will be pseudonymized with a number for each family. Only the CRA at each center will have access to the name and phone number required for the interview, as well as the number corresponding to each family. The correspondence table for the center, populated during the data collection period, will be deleted as soon as the database is frozen.

These data will be retained for the duration of the study and until the end of data analysis. In accordance with MR004 from CNIL, data must be retained for a maximum of 2 years after the last publication or until the final report is signed before archiving, according to the regulations in force.

12.3 Regulatory Compliance with GDPR

This study falls within the scope of the "Reference Methodology" (MR004) in application of the provisions of Article 54, paragraph 5 of Law No. 78-17 of January 6, 1978, as amended, relating to data processing, files, and freedoms. This amendment was approved by decision on January 5, 2006, and modified on July 21, 2016. This study will be registered in the public catalog of studies within the HDH and on the AP-HP registry. Finally, a PIA will be conducted before implementation.

12.4 Archiving

The following documents will be archived under the study name under the responsibility of the coordinating investigator and associated investigators at each center for 15 years:

- Protocol and appendices, any amendments,
- Individual data (authenticated copies of raw data),
- Monitoring documents and correspondence related to the research.

The sponsor is also responsible for organizing the retention of statistical analyses and the final study report during the regulatory archiving period. No transfer or destruction may be carried out without the sponsor's agreement. At the end of the 15 years, the sponsor will be consulted regarding destruction. All data, documents, and reports may be subject to audit or inspection.

